6.1.5 DOSING AND ADMINISTRATION

A pharmacist or other qualified individual will be identified at each site to prepare Cemiplimab-rwlc for administration. The planned dose and schedule of Cemiplimab-rwlc is 350 mg IV over approximately 30 minutes every 21 days (+/- 3 days).

Storage of Infusion Solution:

- Store at room temperature up to 25 °C (77 °F) for no more than 8 hours from the time of preparation to the end of the infusion or at 2 °C to 8 °C (36 °F to 46 °F) for no more than 24 hours from the time of preparation to the end of infusion.
- Allow the diluted solution to come to room temperature prior to administration.
- Do not freeze.

Administration:

- Administer by intravenous infusion over 30 minutes through an intravenous line containing a sterile, in-line or add-on 0.2 micron to 5-micron filter.

6.1.6 ROUTE OF ADMINISTRATION

Cemiplimab-rwlc will be administrated intravenously.

6.1.7 STARTING DOSE AND DOSE ESCALATION SCHEDULE

Cemiplimab-rwlc is administered as a flat dose of 350 mg IV over approximately 30 minutes every 21 days (+/- 3 days).

6.1.8 DOSE ADJUSTMENTS/MODIFICATIONS/DELAYS

Patients will remain on the dosage of Cemiplimab-rwlc throughout the course of study treatment. Dose reduction is not allowed. The dose will be held until the resolution of the adverse events as below.

Adverse events (AEs) are to be reported according to the National Cancer Institute Common Terminology Criteria for Adverse Events (NCI-CTCAE) version 5. Patients who experience grade ≥ 3 treatment-related toxicity (excluding laboratory abnormalities that are considered clinically insignificant) that is not otherwise specified in the protocol will be required to temporarily discontinue treatment with Cemiplimab-rwlc. Such patients may be considered for resumption of treatment once the toxicity resolves to grade 1 or baseline, or when the toxicity is stable and manageable through supportive/medical therapy (eg, grade 3 hypertension that can be controlled with addition of a second anti-hypertensive agent) per the CTCAE version 5.

Holding of treatment due to an AE or a missed visit if a patient is hospitalized is not a violation. If a patient is able to come in for a study visit according to the visit schedule, but does not receive Cemiplimab-rwlc, the visit should be entered into the database. The protocol assessments required at the visit (ie, labs, physical exam) should still be completed as far as possible and the data entered at the appropriate visit in the electronic case report form (CRF). If the patient is not able to come in for a study visit, according to the study schedule, the visit should be skipped. If a scan was missed as part of the skipped visit, the response assessment will be performed prior to resuming treatment and subsequent scans will be performed in line with the original schedule.

Upon occurrence of a study treatment-related event at any time on the study, resumption of treatment after resolution or stabilization of the condition is allowed at the discretion of the investigator if resuming treatment is thought to be in the best interest of the patient, with the exception of the following categories:

- Patients with events that require Cemiplimab-rwlc to be discontinued for more than 84 days from last scheduled dose.
- Patients with grade ≥ 2 uveitis. Patients with grade 2 uveitis will generally be discontinued from study treatment, unless there is resolution to grade ≤ 1 AND discussion with and approval by the site principal investigators. All patients with grade ≥ 3 uveitis will be permanently discontinued from study treatment.

After other AEs, resumption of treatment may be at the initial dose level. A patient who does not

tolerate Cemiplimab-rwlc will be removed from the study. Refer to [Appendix 1](#) for additional management guidelines for immune-related toxicities.

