5.4 PARTICIPANT WITHDRAWAL OR TERMINATION

5.4.1 REASONS FOR WITHDRAWAL OR TERMINATION

Participants are free to withdraw from participation in the study at any time upon request. The study investigator or the funding source of the study ("Regeneron") can remove participants from the study without their consent at any time for any reason including:

- If any treatment-related Grade 4 adverse events (AE) develops during Cemiplimab-rwlc therapy.
- If any clinically adverse event (AE), laboratory abnormality, or other medical condition or situation occurs such that continued participation in the study would not be in the best interests of the participant.

- If the participant meets any exclusion criteria (either newly developed or not previously recognized) that precludes further study participation.
- Extraordinary medical circumstances: If at any time the constraints of this protocol are detrimental to the patient's health, the protocol treatment should be discontinued.
- If patient develops progressive disease, then the patient will discontinue the protocol therapy.
- If patient develops unacceptable toxicity, then the patient will discontinue the protocol therapy.

The reason and date for patient removal from the study must be documented in the Case Report Form (CRF).

The same procedures will be followed as those that would happen if participants decided to discontinue from the study.

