Grade 2 Requires infusion interruption but responds promptly to symptomatic treatment (i.e., antihistamines, NSAIDS, narcotics, IV fluids); prophylactic medications indicated for ≤ 24 hours	
Stop infusion and monitor symptoms.
 
Additional appropriate medical therapy may include but is not limited to:
 
• IV fluids• Antihistamines• NSAIDS• Acetaminophen• Narcotics 
Increase monitoring of vital signs as medically indicated until the patient is deemed medically stable in the opinion of the investigator.
 
If symptoms resolve within one hour of stopping drug infusion, the infusion may be restarted at 50% of the original infusion rate.
 
Otherwise, dosing will be held until symptoms resolve, and the patient should be premedicated for the next scheduled dose.
 
Patients who develop Grade 2 toxicity despite adequate premedication should be permanently discontinued from further trial treatment administration.
	Subject may be premedicated 1.5h (\pm 30 minutes) prior to infusion of cemiplimab with: 
• Diphenhydramine 50 mg PO (or equivalent dose of antihistamine)• Acetaminophen 500-1000 mg PO (or equivalent dose of antipyretic)

Grade 3 or 4 Grade 3: Prolonged (i.e., not rapidly responsive to symptomatic medications and/or brief interruption of infusion); recurrence of symptoms following initial improvement; hospitalization indicated for other clinical sequelae (e.g., renal impairment, pulmonary infiltrates) Grade 4: Life-threatening; pressor or ventilatory support indicated	
Stop infusion.
 
Additional appropriate medical therapy may include but is not limited to:
 
• IV fluids• Antihistamines• NSAIDS• Acetaminophen• Narcotics• Oxygen• Pressors• Corticosteroids• Epinephrine 
Increase monitoring of vital signs as medically indicated until the patient is deemed medically stable in the opinion of the investigator.
 
Hospitalization may be indicated.
 
Patient is permanently discontinued from further trial treatment administration.
	No subsequent dosing
---	--	----------------------

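### Section 6.1.8's resumption rule omits four permanent stops set elsewhere and conflicts with the action column of Appendix 1's Grade 3-4 uveitis row, and no text says which rule governs

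*Combined protocol and SAP*

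**What the plan says.** Section 6.1.8 gives a general permission. After a treatment-related event that has resolved or stabilized, "resumption of treatment after resolution or stabilization of the condition is allowed at the discretion of the investigator", on condition that resuming is thought to serve the patient's best interest. The permission is given "with the exception of the following categories", and two categories follow. One is an event that keeps the patient off drug for more than 84 days from the last scheduled dose. The other is uveitis of Grade 2 or higher. Grade 2 has a route back through resolution and site PI approval. Grade 3 and above has none: "All patients with grade ≥ 3 uveitis will be permanently discontinued from study treatment". The section then adds: "After other AEs, resumption of treatment may be at the initial dose level". It closes by sending the reader to Appendix 1 for "additional management guidelines for immune-related toxicities" and does not mention Table 4.

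Other parts of the protocol set stops for particular events. For a Grade 3 or 4 infusion reaction, Table 4 in Section 7.8 says: "Patient is permanently discontinued from further trial treatment administration". It also stops the drug for good after a Grade 2 infusion reaction that occurs despite premedication. Appendix 1 has its own stops for enterocolitis, skin events, pneumonitis and uveitis.

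Some general rules also bear on the point. Section 5.4.1 says: "If patient develops unacceptable toxicity, then the patient will discontinue the protocol therapy". It also names treatment-related Grade 4 events among the reasons for which the investigator or funder can remove a participant. Section 6.1.8 says that a patient who does not "tolerate Cemiplimab-rwlc will be removed from the study".

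**The concern.** An exception list introduced in this way reads as complete. An investigator who consults only that list finds no bar to resuming after a Grade 4 skin event or a Grade 3 infusion reaction, although other parts of the protocol stop the drug permanently. For Grade 3-4 uveitis the position is reversed: 6.1.8 closes the door and a line in Appendix 1 appears to reopen it.

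What is at stake is re-exposure after serious toxicity, and whether the six sites treat the same event alike. The Grade 4 skin row covers Stevens-Johnson syndrome and toxic epidermal necrolysis. Section 2.3.1 gives toxic epidermal necrolysis as the cause of one of five deaths associated with cemiplimab as of January 2017. Section 2.1 says that the drug's safety in this population is unknown.

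**Working it through.** The check is textual. Each event-specific stop is set against the two exceptions in 6.1.8.

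| Event | Source | Rule in that source | Among the 6.1.8 exceptions? |
|---|---|---|---|
| Infusion reaction, Grade 3-4 | 7.8, Table 4 | Permanent stop | No |
| Infusion reaction, Grade 2 despite premedication | 7.8, Table 4 | Permanent stop | No |
| Enterocolitis, Grade 3 | Appendix 1, Grade 3-4 colitis row | Action column: permanent stop; dosing column: hold | No |
| Skin events, Grade 4 | Appendix 1 | Permanent stop | No |
| Pneumonitis, Grade 3-4 | Appendix 1 | Discontinue, no restart terms | No |
| Pneumonitis, second episode of Grade 2 or higher | Appendix 1 | Discontinue, no restart terms | No |
| Uveitis, Grade 2 | Appendix 1 | Resumption with site PI approval after resolution | Yes, and the texts agree |
| Uveitis, Grade 3-4 | Appendix 1 | Dosing column: discontinue; action column: terms for resumption | Yes, as permanent; the action column conflicts |
| Renal events, Grade 3-4 | Appendix 1 | Dosing column: discontinue; action column: restart possible | No, and not counted as a final stop |

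**Count.** Stops worded as permanent and absent from 6.1.8: 2 (Table 4) + 1 (enterocolitis) + 1 (skin) = 4. Adding the two pneumonitis stops gives 4 + 2 = 6. The list itself has 2 exceptions.

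**Omission or contradiction.** For the six missing stops, 6.1.8 permits in general terms and does not name the event, while the other text forbids. An investigator who does not resume complies with both. Grade 3-4 uveitis is different, because both texts address the same event and grade. 6.1.8 rules out resumption. The action column says how to obtain approval for it, repeating a line that fits the Grade 2 row.

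**Which rule governs.** No text says.

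- 6.1.8 points to Appendix 1. Appendix 1 calls itself guidance and points back to the dose-modification section.
- 6.1.8 does exempt toxicity specified elsewhere in the protocol, but only from the temporary-hold rule for Grade 3 and above. The exemption does not extend to the later resumption sentence.
- The text before Table 4 lets sites use institutional standards for infusion reactions if the treating physician accepts them. It does not say whether the permanent stops survive that choice.
- A simple ranking would not help. If Appendix 1 outranks 6.1.8, resumption after Grade 3-4 uveitis opens. If 6.1.8 outranks the rest, the six stops become discretionary.

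**Rows unclear in themselves.** The Grade 3-4 colitis row holds the drug in one column and stops it permanently for Grade 3 enterocolitis in the other, and it does not name Grade 4 enterocolitis. The Grade 3-4 renal row discontinues and then allows a restart.

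**Statistical design.** Section 10.5 reproduces. With success at 7 or more responses of 27, exact binomial alpha at P0 = 0.15 is 0.0986, and power at P1 = 0.15 + 0.18 = 0.33 is 83.8%. No dosing rule enters either figure.

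**The case against.** The strongest reply is that these rules can be read together. The 6.1.8 permission is discretionary and conditional on the patient's best interest, so it gives no one a right to rechallenge. The sentence on other AEs concerns dose level, in keeping with the ban on dose reduction, and does not widen who may resume. A reader who follows 6.1.8 to its end is sent to Appendix 1 and finds the Grade 4 skin stop there. Section 5.4.1 adds treatment-related Grade 4 events as a ground for removal. In the uveitis row the dosing column agrees with 6.1.8. Monthly site teleconferences, monthly review by the Protocol Monitoring Committee (8.6) and the halting rule after three probably related Grade 3 events (8.5) also help consistency.

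Most of this stands, and it limits the point. A reader might infer that the protocol endorses rechallenge after toxic epidermal necrolysis or a life-threatening infusion reaction. The documents do not support that: specific text stops the drug in both cases, and 6.1.8 never requires resumption.

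The reply leaves four gaps. The Grade 4 ground is permissive and does not reach Grade 3 infusion reactions, Grade 3 pneumonitis or the Grade 2 stops. The rules on unacceptable toxicity and intolerance carry no grade. 6.1.8 does not lead the reader to Table 4. Oversight after the event does not tell an investigator which text to follow beforehand.

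**Conclusion.** The point holds as a low-severity correction for safety and consistency. Four permanent stops are missing from the 6.1.8 exceptions, or six if the pneumonitis stops are final. There is one direct contradiction, confined to the action column of the Grade 3-4 uveitis row. Two further rows, colitis and renal at Grade 3-4, do not give a single dosing rule.

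This rests on two readings: that the 6.1.8 list is meant to be complete, and that discontinuing for pneumonitis without restart terms is meant as final. The second is reasonable but not stated.

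How often the conflict would arise cannot be estimated. Section 2.3.1 gives frequency bands not broken down by grade, and five deaths without the number treated. A reader might also infer consequences for the trial's inference. There are none for sample size, alpha or power, and nothing in the documents supports an effect on the response rate.

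**What to change.** 1. Delete the resumption line from the Grade 3-4 uveitis row of Appendix 1. Keep it in the Grade 2 row.
2. Add a sentence to 6.1.8 that event-specific permanent stops in Table 4 and Appendix 1 override the general permission to resume, with a cross-reference to Table 4. Name the two pneumonitis stops there once the clinical team confirms that they are final.
3. State in 7.8 that using institutional standards for infusion reactions does not waive Table 4's permanent stops.
4. Have the clinical team set one dosing rule for Grade 3-4 enterocolitis and one for Grade 3-4 renal events.

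The cost is a wording amendment, the IRB review that Section 13.2 requires for it, and a memo to sites. No extra patients or data are needed. The real downside is the loss of discretionary rechallenge for a responding patient whose listed event has resolved.

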6.1.9 DURATION OF THERAPY

Patients will be treated for 1 year (17 cycles) unless they have disease progression, intolerable toxicities or withdraw consents.

6.1.10 TRACKING OF DOSE

Cemiplimab-rwlc will be administered at the study site and recorded on the electronic CRF. All dosing records for each patient will be kept by the site. All drug compliance records must be kept current and must be made available for inspection by the lead site and regulatory agency inspectors.

6.1.11 DEVICE SPECIFIC CONSIDERATIONS

Not Applicable

6.2 STUDY AGENT ACCOUNTABILITY PROCEDURES

All drug accountability records must be kept current. The investigator must be able to account for all opened and unopened study drug. These records should contain the dates, quantity, and study medication dispensed to each patient, returned from each patient (if applicable), and disposed of at the site or returned to Regeneron Pharmaceuticals Inc. All accountability records must be made available for inspection by the lead site and regulatory agency inspectors; photocopies must be provided to the lead site at the conclusion of the study.

7 STUDY PROCEDURES AND SCHEDULE

7.1 STUDY PROCEDURES/EVALUATIONS

7.1.1 STUDY-SPECIFIC PROCEDURES

Not Applicable

7.1.2 STANDARD OF CARE STUDY PROCEDURES

Standard of care procedures obtained during the study:

- Medical history.
- Medication history.
- Physical examination.
- Radiographic, photographic, or other imaging assessments.
- Laboratory evaluations.
- Assessment of therapy adherence.

7.2 LABORATORY PROCEDURES/EVALUATIONS

7.2.1 CLINICAL LABORATORY EVALUATIONS

Table 1. Clinical laboratory tests

Category	Tests
Laboratory tests	CBC w/differential (hemoglobin, hematocrit, WBC with differential count, platelet count) CMP (Sodium, potassium, bicarbonate, chloride, BUN, creatinine, total bilirubin, ALT, AST). Magnesium INR (only as part of the screening assessment or if clinically indicated) Amylase, lipase Hepatitis testing for only research purposes will not be performed, but documented if the status is known. HIV CD4 count as a standard of care
Pregnancy test	Serum or urine β -hCG (for women of childbearing potential)
Thyroid panel	TSH and free T4

ALT= alanine aminotransferase, AST=aspartate aminotransferase, β -hCG = beta-human chorionic gonadotropin, BUN=blood urea nitrogen CBC=complete blood count, CMP=comprehensive metabolic panel, INR = International Normalized Ratio, TSH= thyroid stimulating hormone, T4 = thyroxine, WBC=white blood cells.

7.2.2 OTHER ASSAYS OR PROCEDURES

Patients from the parent study will be eligible for participation on an optional basis in a tissue biomarker study and the blood collection for the biomarker correlative study.

In all study participants, submission of archived diagnostic formalin fixed paraffin embedded (FFPE) tumors obtained at any time prior to Cemiplimab-rwlc treatment is required. Additionally, tumor tissue will be obtained from the most accessible locations for a biopsy prior to initiation and at the end of Cemiplimab-rwlc therapy. These biopsies for only research purposes are OPTIONAL. Any metastatic cancer tissue obtained during the study (including but not limited to excisional, core biopsies, surgical specimens, etc.) will be subject to additional molecular studies in the future.

PROPOSED BIOMARKER EVALUATIONS

7.2.2.1 *Determination of the genomic landscape to determine tumor mutation burden*

The archived FFPE primary tumors (and subsequent metastatic tumors if available) will be analyzed by whole exome sequencing, and the comprehensive genomic landscape and tumor mutation burden will be assessed.

7.2.2.2 *Evaluation of the Tumor Immune Microenvironment*

Intact immune system is critical for tumor surveillance. Comprehensive evaluation of tumor immune microenvironment has not been fully characterized. An innovative methodology, multiplex immune-histochemical (mIHC) staining, allows the analysis of an array of markers from limited sample specimens. The evaluation of a complex cellular microenvironment is best accomplished using mIHC which enables simultaneous detection and measurement of multiple protein antigens on the same tissue section allowing accurate classification of cells as well as enumeration and quantification of

protein signal. This is accomplished by using sequential steps of primary antibody application, scanning the image, and then antibody stripping. The process is repeated using each antibody target. The result is that up to 20 protein targets can be visualized. This complex staining can then be analyzed by imaging systems such as the Aperio scanning system. Image analysis software can then be applied to enumerate cells and quantify signal. Complex analysis can determine cellular densities and also measure co-localized targets. The multiplexing will encompass evaluation of antigen presenting cells, T cells, B cells, macrophages, and tumor cells. The goal is to link a comprehensive clinical characterization and immune microenvironment assessment and to correlate these with Cemiplimab-rwlc treatment response and survival.

7.2.2.3 Detection of Circulating Tumor DNA in Plasma and Its Association With Cemiplimab-rwlc response

Determination of early response to Cemiplimab-rwlc by conventional imaging studies can be difficult. Circulating tumor DNA in pre- and post-treatment plasma has been shown to track with the disease burden.¹⁷ We will determine the presence of a unique genomic alteration found in each patient based on the whole exome sequencing of their tumor and identify the presence of the alterations in circulating tumor DNA. Quantity of circulating tumor DNA in the plasma compared with at pre-treatment and at end of treatment will be correlated with the response determined by the imaging studies.

7.2.3 SPECIMEN PREPARATION, HANDLING, AND STORAGE

SPECIMEN PREPARATION, HANDLING, AND STORAGE

Tissue specimens will be handled and stored according to the Laboratory Manual.

Tissue/Specimen Submission

Tumor tissue samples will be collected at pre- and post-treatment. The tumor tissue samples will be submitted to the Moffitt Tissue Core for banking and translational research.

Pre-treatment formalin-fixed paraffin-embedded (FFPE) archived tumor samples (MANDATORY)

Any archived tumor tissue (except FNA cell blocks) obtained before Cemiplimab-rwlc is allowed. An FFPE tumor block should be submitted with the submission form. A Pathology Report and one hematoxylin and eosin-stained slide documenting that the submitted block or unstained slides contain tumor should also be submitted with the tissue. The report and hematoxylin and eosin-stained slide must include the protocol number and patient's case number. The patient's name and/or other identifying information should be removed from the report. The surgical pathology numbers and information must NOT be removed from the report.

Pre- and post-treatment tumor biopsy (Day -21 to 0 before Cemiplimab-rwlc and at the End of Treatment visit; OPTIONAL)

The pre- and post-treatment tumor biopsy can be obtained from the primary site, lymph node metastasis, or other safely accessible site metastases as a punch biopsy or a core needle biopsy: one punch or core in formalin and the second punch or core in liquid nitrogen (or dry ice/ethanol slurry). The biopsy sample should be prepared: 1) as a formalin-fixed paraffin-embedded tumor block and 2) as a flash frozen sample in liquid nitrogen (or dry ice/ethanol slurry). The frozen specimens can be stored at -80°C (-70°C to -90°C).

CORRELATIVE WITH BLOOD

Blood samples must be submitted with the submission form documenting the date of collection of the sample; the protocol number, the patient's case number, time point of study, and method of storage (for example, stored at -80°C). The frozen specimens can be stored at -80°C (-70°C to -90°C).

The blood samples should be processed as detailed in the Laboratory Manual.

In brief,

1 x 10 ml Lavender EDTA tube and 1 x 8.5 ml LBgard tube of blood will be generated from each clinical event. The samples will be processed and shipped according to the Laboratory Manual.

Clinical events:

1. Pre-therapy (Anytime between Day -21 and Cycle 1 Day 1)
2. Cycle 3 Day 1 +/- 7 days
3. Cycle 6 Day 1 +/- 7 days
4. Cycle 9 Day 1 +/- 7 days
5. Cycle 12 Day 1 +/- 7 days
6. End of treatment +/- 7 days
7. End of study +/- 7 days

Collection procedure:

- Draw one 10 ml Lavender EDTA tube and one 8.5 ml LBgard Blood Tube.
- Draw the EDTA tube first and then LBgard Blood Tube second.
- Completely fill the LBgard Blood Tube.
- When draw the LBgard Blood Tube, follow the steps below to avoid possible backflow of chemical additives from the tube.
 - Place the subject's arm in a downward position.
 - Hold tube in vertical position, below the donor's arm during blood collection.
 - Release tourniquet as soon as blood starts to flow into tube.
 - Ensure that tube additives do not contact stopper or end of needle during venipuncture.
- Ensure that the blood has stopped flowing into the tube before removing the tube from the holder.
- Immediately after blood draw, gently invert the LBgard Blood Tube ten times.
- **The blood samples should be processed within 2 hours from collection.**
- **If the blood samples cannot be processed within 2 hours from collection due to lack of institutional facility, draw the second LBgard blood tube in place of the EDTA tube and ship without any processing within 24 hours in room temperature.**

Table 2. Specimen collection summary for correlative studies (Samples can be batched and sent in one shipment)

Specimens taken from patient:	Collected when:	Stored as:
Archived paraffin-embedded tissue of the primary tumor taken any time before initiation of Cemiplimab-rwlc treatment (Mandatory)	Pre-treatment	Paraffin-embedded tissue block. Refer to the Laboratory Manual.
Fresh frozen tissue of the primary or metastatic tumor taken before initiation of Cemiplimab-rwlc treatment (for research purposes only: OPTIONAL)	Pre-treatment	Frozen tumor in a 2 mL cryovial. Refer to the Laboratory Manual.
A paraffin-embedded tissue of	Pre-treatment and Post-treatment	Paraffin-embedded

the primary or metastatic tumor (for research purposes only: OPTIONAL)	taken: 1) during Day -21 to 0 before Cycle 1 Day 1 of Cemiplimab-rwlc, and 2) at the End of Treatment visit	tissue block. Refer to the Laboratory Manual.
Fresh frozen tissue of the primary or metastatic tumor (for research purposes only: OPTIONAL)	Post-treatment taken at the End of Treatment visit	Frozen tumor in a 2 mL cryovial. Refer to the Laboratory Manual.
PLASMA: 18.5 mL of anticoagulated whole blood in EDTA tube (purple/ lavender top) and LBgard tube	Pre-treatment and post-treatment taken: 1) during Day -21 to 0 before Cemiplimab-rwlc 2) Cycle 3 Day 1 +/- 7 3) Cycle 6 Day 1 +/- 7 4) Cycle 9 Day 1 +/- 7 5) Cycle 12 Day 1 +/- 7 6) End of Treatment +/- 7 days 7) End of Study +/- 7 days	Frozen plasma samples 3 to 5 labeled 2 ml size Nunc cryovial with 1.5 ml of plasma each. Refer to the Laboratory Manual.
PBMC: 18.5 mL of anticoagulated whole blood in EDTA tube (purple/ lavender top) and LBgard tube. Collect PBMC and buffy coat after collecting plasma.	Pre-treatment and post-treatment taken: 1) during Day -21 to 0 before Cemiplimab-rwlc 2) Cycle 3 Day 1 +/- 7 3) Cycle 6 Day 1 +/- 7 4) Cycle 9 Day 1 +/- 7 5) Cycle 12 Day 1 +/- 7 6) End of Treatment +/- 7 days 7) End of Study +/- 7 days 7 days	3 to 5 labeled 2 ml size Nunc cryovial with ~2-3 million of PBMC cells in each cryovial. Refer to the Laboratory Manual.

